## 2 LIST OF ABBREVIATIONS AND DEFINITIONS OF TERMS

Abbreviation	Term
AChEI	Acetylcholinesterase inhibitor
AD	Alzheimer's disease
ADAS-cog	Alzheimer's Disease Assessment Scale - cognitive subscale
AE	adverse event
ApoE	Apolipoprotein E
BMI	body mass index
BP	blood pressure
CBB	CogState Brief Battery
C-CASA	Columbia- classification algorithm of suicide assessment
CDR	Clinical Dementia Rating
CRF	case report form
C-SSRS	Columbia Suicide Severity Rating Scale
ECG	electrocardiogram
ED	early discontinuation
eCRF	electronic case report form
FAQ	functional assessment questionnaire
FAS	full analysis set
INR	international normalized ratio
ISLT	International Shopping List Task
LLT	Lower level term
MCI	mild cognitive impairment
MedDRA	Medical Dictionary for Regulatory Activities
MMSE	mini-mental state examination
MRI	magnetic resonance imaging
OLE	open-label extension
PD	pharmacodynamic
PT	Preferred term

---

Abbreviation	Term
SAE	serious adverse event
SAP	statistical analysis plan
SAS	safety analysis set
SD	standard deviation
SI	Système International
SOC	System organ class
TEAE	treatment-emergent adverse event
TEMAV	treatment-emergent markedly abnormal laboratory values
TLG	tables, listings, and graphs
vMRI	Volumetric magnetic resonance imaging
WHO DD	World Health Organization Drug Dictionary

### 3 INTRODUCTION

The purpose of this statistical analysis plan (SAP) is to describe the procedures and the statistical methods that will be used to analyze and report results from Open-label Extension (OLE) phase of study E2609-G000-202. This SAP is based on the protocol amendment 08 and “study” indicates OLE phase unless specifically described.

#### 3.1 Study Objectives

##### 3.1.1 Primary Objective(s)

- To assess the long-term safety and tolerability of daily dosing with elenbecestat (E2609) 50 mg in mild cognitive impairment (MCI)/Prodromal subjects and in subjects with mild to moderate dementia due to Alzheimer's disease (AD)

##### 3.1.2 Secondary Objective(s)

- To explore the long-term effects of elenbecestat on clinical status by assessment of:
  - a. The Mini-Mental State Examination (MMSE)
  - b. The Functional Assessment Questionnaire (FAQ; also known as the Functional Activities Questionnaire)
- To explore the long-term effects of elenbecestat on:
  - a. Volumetric magnetic resonance imaging (vMRI) including, but not limited to, total hippocampal volume, left and right hippocampal volume, whole brain volume, and total ventricular volume at 24 and 48 months of treatment in the Extension Phase.
  - b. Plasma amyloid at 12, 24, 36, and 48 months of treatment in the Extension Phase

#### 3.2 Overall Study Design and Plan

The Extension Phase allows eligible subjects to receive elenbecestat 50 mg for up to 48 months (4 years).

Subjects who are enrolled in the Core Study will have the option to participate in the Extension Phase provided that they complete the Core Study (which includes 18 months of double-blind treatment and 12 weeks of Follow-up Period) and satisfy the entry criteria for the Extension Phase. Subjects who discontinue from study drug during the Core Study are not eligible to participate in the Extension Phase.

Eligible subjects who choose to participate in the Extension Phase may enter the Extension Phase immediately following the completion of Visit 20 (ie, Visit 21 procedures may be completed on the same day as Visit 20). Subjects who are eligible to participate in the Extension Phase but

who do not transition to the Extension Phase on the day of Visit 20 may enter the Extension Phase any time within 4 weeks of Visit 20. The Medical Monitor must be contacted if Visit 21 is to occur more than 4 weeks after Visit 20. For all subjects, assessments performed at V20 may serve as baseline values for the Extension Phase (ie, results of assessments conducted at Visit 21) with exceptions of laboratory assessments and vital signs, which must be repeated if Visit 21 occurs more than 10 days from Visit 20.

During the Extension Phase, subjects will receive open-label elenbecestat 50 mg per day for up to 48 months. Subjects with pending International Normalized Ratio (INR) and serum pregnancy test results (females subjects of child bearing potential only) but who are otherwise qualified may begin OLE dosing at Visit 21; however, these subjects must discontinue study drug treatment immediately if either test result meet the exclusion criteria.

Safety assessments will be performed as described in [Table 14 of the protocol](#). Subjects may discontinue from study drug for any reason. Subjects who complete 48 months of the Extension Phase treatment or who discontinue the study drug must comply with the Early Discontinuation Visit (within 7 days after the last dose of study drug) and the Follow-Up Visits (weeks 4 and 12 after the last dose of study drug).

The study will end when the last visit for the last subject has completed the Extension Phase.

## 4 DETERMINATION OF SAMPLE SIZE

Subjects who complete the Core Study will have the option to participate in the Extension Phase. There is no sample size calculation for the Extension Phase.

## 5 STATISTICAL METHODS

All descriptive statistics for continuous variables will be reported using mean, standard deviation (SD), median, minimum and maximum. Categorical variables will be summarized as number (percentage) of subjects.

### 5.1 Study Endpoints

#### 5.1.1 Primary Endpoints

- Safety endpoints: adverse event (AE), vital sign, electrocardiogram (ECG), physical examination, clinical laboratory test, any relevant test of cognitive function to evaluate decline, and magnetic resonance imaging (MRI) parameter (microhemorrhage, vasogenic edema, and other clinically significant abnormalities).

#### 5.1.2 Secondary Endpoints

Changes from Core Study and Extension Phase baselines in

- MMSE and FAQ at each visit assessed in the Extension Phase
- Plasma amyloid measurements at 12, 24, 36, and 48 months of Extension Phase treatment
- vMRI parameters including, but not limited to, total hippocampal volume, left and right hippocampal volume, whole brain volume, and total ventricular volume with up to 24 and 48 months of Extension Phase treatment

Due to the termination of the study, only change from Extension Phase baseline will be summarized and change from Core Study baseline will not be summarized. Percent change from Extension Phase baseline will be summarized if applicable.

## 5.2 Study Subjects

### 5.2.1 Definitions of Analysis Sets

The OLE Safety Analysis Set (OLE-SAS) is the group of subjects who receive at least 1 dose of study drug during the OLE Phase.

The OLE Full Analysis Set (OLE-FAS) is the group of subjects who receive at least 1 dose of study drug during the OLE Phase and have baseline and at least 1 postdose efficacy assessment during the OLE Phase.

The OLE pharmacodynamics (PD) Analysis Set is the group of subjects who have baseline and at least 1 posttreatment PD measurement in the OLE Phase.

### 5.2.2 Subject Disposition

The number of subjects screened, the number (percent) of subjects who failed screening, and the reasons for screen failure will be summarized, based on data reported on the Screening Disposition (OLE phase) electronic case report form (eCRF).

**Study Completion:** The number (percent) of enrolled and treated subjects who completed the study and who withdrew from the study will be summarized according to the primary reason for discontinuation and secondary reason(s) for discontinuation, based on data reported on the Subject Disposition (OLE phase) eCRF. The number (percent) will be presented for treatment group by core study treatment (placebo and elenbecestat total) and combined total; enrolled, not treated, treated, who completed the study, and withdrew from the study. The primary reasons for early withdrawal from the study are: AE, lost to follow-up, subject choice, withdrawal of consent, pregnancy, study terminated by sponsor, and other. The secondary reasons for early withdrawal from the study are: AE, subject choice, and other.

**Completion of Study Treatment:** The number (percent) of randomized and treated subjects who completed study drug and who discontinued from study drug will be summarized according to the primary reason for discontinuation and also according to secondary reason(s) for

discontinuation, based on data reported on both the Subject Disposition (OLE phase) eCRF and Early Discontinuation (ED) from Study Drug (OLE phase) eCRF. The number (percent) will be presented for treatment group by core study treatment (placebo and elenbecestat total) and combined total; enrolled, not treated, treated, who completed study drug, and discontinued from study drug. The primary reasons for early discontinuation from the study drug are: AE, subject choice, inadequate therapeutic effect, pregnancy and other. The secondary reasons for early discontinuation from the study drug are: AE, subject choice, inadequate therapeutic effect, and other.

### 5.2.3 Protocol Deviations

A listing of subjects with protocol deviations will be provided by subject along with the description of the protocol deviation. Protocol deviations will be identified prior to database lock.

### 5.2.4 Demographic and Other Baseline Characteristics

Demographic and other baseline characteristics for the OLE-SAS will be summarized by treatment group by core study treatment (placebo and elenbecestat total) and combined total using descriptive statistics. Continuous demographic and baseline variables include age, weight, body mass index (BMI), Alzheimer's Disease Assessment Scale - cognitive subscale (ADAS-cog14), Clinical Dementia Rating (CDR) Sum of Boxes, MMSE, International Shopping List Task (ISLT) z-score (total recall, delayed recall), CogState Brief Battery (CBB) z-score (accuracy of one-back memory, accuracy of one-card learning, speed of one-back memory, speed of detection, speed of identification), and FAQ; categorical variables include sex, age group ( $\leq 65$  years, age  $> 65$  years), race, ethnicity, Apolipoprotein E4 (*ApoE4*) status (positive or negative), prior treatment with Acetylcholinesterase inhibitors (AChEIs) or memantine at OLE baseline (no or yes), clinical population (MCI/Prodromal AD, mild to moderate AD) at screening in Core Study, and CDR global score

### 5.2.5 Prior and Concomitant Therapy

All investigator terms for medications recorded in the case report form (CRF) will be coded to an 11-digit code using the World Health Organization Drug Dictionary (WHO DD) (May 2014 or higher). All medications will be presented in subject data listings.

### 5.2.6 Treatment Compliance

Percent compliance will be calculated as follows:

Compliance=

$$\frac{\text{Total number of tablets dispensed} - \text{Total number of tablets returned}}{\text{Planned Total number of tablets to be taken}} \times 100\%$$

## 5.3 Data Analysis General Considerations

### 5.3.1 Pooling of Centers

Subjects from all centers will be pooled for all analyses.

### 5.3.2 Adjustments for Covariates

Not applicable.

### 5.3.3 Multiple Comparisons/Multiplicity

Since the primary objective of this study is about safety and tolerability, no multiplicity adjustment will be applied.

### 5.3.4 Examination of Subgroups

Not applicable.

### 5.3.5 Handling of Missing Data, Dropouts, and Outliers

If any item is missing within the MMSE, and FAQ, then their respective total scores will be missing.

For plasma Ab(1-x), values >upper limit of quantification (ULOQ) or < lower limit of quantification (LLOQ) will be imputed using ULOQ or LLOQ respectively.

### 5.3.6 Other Considerations

Not applicable.

## 5.4 Safety Analyses

Safety analysis will be performed similarly to the Core Study. All safety analyses will be based on OLE-SAS. The incidence of AEs, out-of-normal-range laboratory safety test variables, abnormal ECG findings, out-of-range vital signs, suicidality (Columbia Suicide Severity Rating Scale(C-SSRS)), and changes from baseline in laboratory safety test variables, ECGs, safety MRI, vital sign measurements, and cognitive decline assessment such as MMSE will be summarized by using descriptive statistics. The OLE baseline is used for all safety analyses.

### 5.4.1 Extent of Exposure

The extent of exposure to study drug will be summarized by categories of cumulative months as well as by categories of duration of exposure in 3-month intervals. The number and percent of

subjects for each exposure category will be presented for treatment group by core study treatment (placebo and elenbecestat total) and combined total. Duration of exposure is the number of months between the date the subject received the first dose of OLE study drug and the date the subject received the last dose of OLE study drug and will be summarized using descriptive statistics as continuous variable for treatment group by core study treatment (placebo and elenbecestat total) and combined total. Overall exposure (number of subject months) is defined as summation over all subjects' exposure durations in the OLE and will be summarized for treatment group by core study treatment (placebo and elenbecestat total) and combined total.

#### 5.4.2 Adverse Events

The AE verbatim descriptions (investigator terms from the eCRF) will be classified into standardized medical terminology using the Medical Dictionary for Regulatory Activities (MedDRA). Adverse events will be coded to the MedDRA (Version 22.0 or higher) lower level term (LLT) closest to the verbatim term. The linked MedDRA preferred term (PT) and primary system organ class (SOC) will also be captured in the database.

A treatment-emergent adverse event (TEAE) is defined as an AE that emerged during treatment in OLE, having been absent at pretreatment (Baseline) in OLE or

- Reemerged during treatment in OLE, having been present at pretreatment (Baseline) in OLE but stopped before treatment in OLE, or
- Worsened in severity during treatment in OLE relative to the pretreatment state, when the AE was continuous.

Only those AEs that are treatment emergent will be included in summary tables. All AEs, treatment emergent or otherwise, will be presented in subject data listings.

The TEAEs will be summarized for treatment group by core study treatment (placebo and elenbecestat total) and combined total. The incidence of TEAEs will be reported as the number (percentage) of subjects with TEAEs by SOC and PT. A subject will be counted only once within a SOC and PT, even if the subject experienced more than 1 TEAE within a specific SOC and PT. The number (percentage) of subjects with TEAEs will also be summarized by maximum severity (mild, moderate, or severe). The number (percentage) of subjects with TEAEs will also be summarized by relationship to study drug (Yes [related] and No [not related]).

A subject data listing of all AEs leading to death will be provided.

The number (percent) of subjects with treatment-emergent serious adverse events (SAEs) will be summarized by MedDRA SOC and PT for treatment group by core study treatment (placebo and elenbecestat total) and combined total. A subject data listing of all SAEs will be provided.

The number (percent) of subjects with TEAEs leading to discontinuation from study drug will be summarized by MedDRA SOC and PT for treatment group by core study treatment (placebo and

elenbecestat total) and combined total. A subject data listing of all AEs leading to discontinuation from study drug will be provided.

The number (percent) of subjects with TEAEs with specific interest will be summarized by MedDRA SOC and PT for treatment group by core study assignment (placebo and elenbecestat total) and combined total.

The number (percent) of subjects with non-serious TEAEs will be summarized by MedDRA SOC and PT for treatment group by core study assignment (placebo and elenbecestat total) and combined total.

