## 7 CHANGES IN THE PLANNED ANALYSES

Due to the termination of the study, the following analyses, as described in the protocol, will not be performed.

- Summary statistics of change from Core Study baseline in MMSE, FAQ, vMRI parameters, and PD biomarkers
- Figures of change from baseline in MMSE, FAQ, vMRI parameters, and PD biomarkers
- Correlation analysis for the relationship between efficacy endpoints and biomarker endpoints

---

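### TEAEs are reported only as crude percentages, although extension exposure may run from one dose to 48 months and the study was terminated, so the percentages have no defined time horizon

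*SAP*

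**What the plan says.** The primary objective (SAP Section 3.1.1) is "To assess the long-term safety and tolerability of daily dosing with elenbecestat (E2609) 50 mg", and adverse events stand first among the primary safety endpoints in Section 5.1.1.

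On the measure, Section 5.4.2 states: "The incidence of TEAEs will be reported as the number (percentage) of subjects with TEAEs by SOC and PT". It adds: "A subject will be counted only once within a SOC and PT". The tables by maximum severity and by relationship, and those for serious, discontinuation, special-interest and non-serious TEAEs, are also numbers and percentages of subjects, shown by Core treatment (placebo, elenbecestat total) and combined. Section 5.4 bases all safety analyses on the OLE Safety Analysis Set, which Section 5.2.1 defines as the "group of subjects who receive at least 1 dose of study drug during the OLE Phase".

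On time, Section 3.2 states: "During the Extension Phase, subjects will receive open-label elenbecestat 50 mg per day for up to 48 months". Section 5.4.1 tabulates exposure in the same columns and adds a total: "Overall exposure (number of subject months) is defined as summation over all" subjects' extension exposure durations. No adverse event table uses that total or any other person-time denominator.

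Section 7 opens its list of changes with: "Due to the termination of the study, the following analyses, as described in the protocol, will not be performed". The list covers change from Core baseline, figures and correlations. It does not touch the adverse event summaries.

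**The concern.** A crude percentage is a clear measure of risk when everyone is followed for about the same time. This extension offers no such common period. The denominator sets no minimum exposure, the ceiling is 48 months, and termination stops follow-up for reasons unrelated to how long a subject has been on drug. Subjects enter after each completes the Core Study, so unless they all entered together, termination would cut them off at different durations.

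The resulting percentage is neither a 12-month nor a 48-month risk. It is an average over whatever exposure happened to accrue. This applies to the combined column as much as to the prior-placebo and prior-elenbecestat columns, so the point does not depend on any difference between them. At stake is how the main result of a long-term safety phase is read. No test or error rate is involved.

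**Working it through.** The SAP states no event rate, power or sample size for the extension (Section 4), so there is no planned figure to reproduce. The check asks how far a crude percentage moves with exposure alone, at a fixed risk.

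**Inputs from the SAP.** Minimum exposure to be counted: one dose (Section 5.2.1). Maximum: 48 months (Section 3.2). Measure: subjects with an event divided by subjects in the set (Sections 5.4 and 5.4.2).

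**Assumptions, not in the SAP.** A constant hazard *r* of 0.005, 0.02 or 0.05 per month, and in step 2 two invented exposure patterns.

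**Step 1. Everyone followed for *t* months.** Expected crude percentage = 1 − exp(−*rt*).

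| *r* per month | 3 months | 12 months | 24 months | 48 months |
|---|---|---|---|---|
| 0.005 | 1.5% | 5.8% | 11.3% | 21.3% |
| 0.02 | 5.8% | 21.3% | 38.1% | 61.7% |
| 0.05 | 13.9% | 45.1% | 69.9% | 90.9% |

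For example, at *r* = 0.02 and *t* = 12: 1 − exp(−0.24) = 21.3%.

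**Step 2. Exposure varying uniformly from *a* to *b* months.** Expected crude percentage = 1 − [exp(−*ra*) − exp(−*rb*)] / [*r*(*b* − *a*)]. At *r* = 0.02:

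- 0 to 24 months: 1 − (1 − 0.6188)/0.48 = 20.6%.
- 24 to 48 months: 1 − (0.6188 − 0.3829)/0.48 = 50.9%.

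The risk is identical in both. Mean time at risk to first event or end of exposure equals the crude proportion divided by *r*: 0.2058/0.02 = 10.29 months and 0.5086/0.02 = 25.43 months. The first-event rate is then 0.2058/10.29 = 0.5086/25.43 = 2.0 per 100 subject-months in both.

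**Step 3. Could the subject-months of Section 5.4.1 serve as denominator?** That total includes time after the first event. Mean exposure is 12 and 36 months in the two patterns, so subjects with an event per 100 subject-months are:

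| *r* per month | True rate per 100 | 0–24 months | 24–48 months |
|---|---|---|---|
| 0.005 | 0.50 | 5.77/12 = 0.48 | 16.42/36 = 0.46 |
| 0.02 | 2.00 | 20.58/12 = 1.71 | 50.86/36 = 1.41 |
| 0.05 | 5.00 | 41.77/12 = 3.48 | 82.46/36 = 2.29 |

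The shortcut is close for uncommon events and poor for common ones. Any TEAE is likely to be a common event.

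**The case against.** The strongest defence is that the tables are valid as descriptions. Section 5.4 plans descriptive statistics only, there is no test, and a percentage of treated subjects correctly states what was observed. It does not claim to be a 48-month risk. Section 5.4.1 gives 3-month exposure categories, duration and total subject-months in the same columns, so a reader can see an imbalance and form a rough rate, which step 3 shows to be adequate for rare events. All adverse events are also listed by subject.

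Most of this stands. It limits the point to interpretation and shows that partial context is already planned. It does not give the percentage a time horizon, and the published totals do not let a reader form a proper first-event rate for common events.

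A reader might also infer that exposure did vary from days to 48 months, or that the two prior-treatment columns differ in follow-up and so cannot be compared. The SAP supports neither. The range is what the design permits, no observed exposure or termination date is given, both columns receive the same open-label drug after completing the Core Study, and no formal comparison between columns or with the Core phase is planned.

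Nor does the SAP support saying that the percentages understate risk. With truncated follow-up they fall below the 48-month cumulative incidence, but they do not purport to estimate it, and a person-time rate cannot recover unobserved late risk without assuming a constant hazard.

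**Conclusion.** The point holds as a matter of interpretation. Section 5.4.2 gives the leading primary safety endpoint a measure that depends on exposure length as well as risk, in a terminated phase with no common follow-up period, and Section 7 does not adapt it. The size of the distortion cannot be determined from the SAP. Under the assumed constant hazards of 0.005 to 0.05 per month, crude incidence is about 6% to 45% at 12 months and 21% to 91% at 48 months. These figures show how sensitive the measure is and do not estimate the effect in this trial. The change is worthwhile because it is cheap. Without it the tables remain correct counts with an unclear meaning.

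**What to change.** Keep all crude tables in Section 5.4.2 and add two things.

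1. For overall, serious, discontinuation and special-interest TEAEs, by column and combined: exposure-adjusted incidence rate = subjects with a first event / subject-time at risk. Time at risk runs from first extension dose to the first event of that category, or otherwise to a stated end of the treatment-emergent period. Section 5.4.2 defines that period only as during treatment, so its end must be fixed. Give an exact Poisson 95% interval for these category totals. Rates for individual SOCs and PTs are optional, and intervals for them are not needed.
2. One table of TEAE incidence by exposure interval (for example 6-month blocks), with the number at risk at the start of each block.

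Do not use the total subject-months of Section 5.4.1 as the denominator for common events. List the addition in Section 7 next to the other consequences of termination.

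Cost: modest extra programming. First- and last-dose dates are already needed for Section 8.4, but time to first event per category is a new derivation. The rate assumes a roughly constant hazard, and the interval table lets readers judge whether that is reasonable.
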